# **Glossary of Abbreviations**

BOOST	Better Operative Outcomes Software Tool
CF	Counting fingers
COS	Chinese Ophthalmic Society
CPD	Continuing professional development
CSR	Cataract surgical rate
FRCOphth	Fellow of the Royal College of Ophthalmologists (UK)
GCP	Good Clinical Practice
IAPB	International Agency for the Prevention of Blindness
ICEH	International Centre for Eye Health
ICC	Intraclass correlation coefficient
ICO	International Council of Ophthalmology
ITT	Intention-to-treat
LSHTM	London School of Hygiene & Tropical Medicine
LOCS	Lens opacities classification system
LMIC	Low & middle income countries
MD	Medical Doctor
MEd	Masters in Education
МОН	Ministry of Health
MOU	Memorandum of Understanding
MPH	Masters in Public Health
NEI	National Eye Institute
NY	New York
OLIMPICS	Ophthalmic Learning & Improvement Initiative in Cataract Surgery
OSCAR	Ophthalmology Surgical Competency Assessment Rubric
OSSCAR	Ophthalmic Simulated Surgical Competency Assessment Rubric
PCR	Posterior capsule rupture
PI	Principal investigator
POD	Post-operative Day
QUB	Queen's University Belfast
PRECOG	Prospective Review of Early Cataract Outcomes and Grading Study
RCT	Randomised controlled trial
SDP	Sustained deliberate practice
SICS	Small-incision cataract surgery
SOS	Simulated ocular surgery
STEER	Orbis/Chinese Ophthalmic Society Rural Training Program
TREE	Translational Research for Equitable Eyecare
UK	United Kingdom
USA	United States of America
VA	Visual acuity
VFQ	Visual Functioning Questionnaire
VL	Vitreous loss
WHO	World Health Organisation

# Keywords

Simulation, Surgical Education, Training, China, Cataract, Ophthalmic, Randomized Trial, Model Eye

# **General Information**

### **Project Title**

A Randomized Trial of Low-Cost Model Eyes for Cataract Surgical Training of Rural Chinese Ophthalmologists: The China OLIMPICS (Ophthalmic Learning & Improvement Initiative in Cataract Surgery) Trial

### Identifying numbers

Beijing Tongren Hospital Research Ethics Committee: TRECKY2017-046
Queen's University Belfast Research Ethic Committee:
London School of Hygiene & Tropical Medicine:
ClinicalTrials.gov ID: NCT03458442 (date of registration: 1 March 2018)

# **Executive Summary**

The leading cause of blindness in China and the world more generally is un-operated cataract. Despite notable efforts on the part of the Chinese government, China's cataract surgical rate (1400/million/year in 2015) remains lower than that of many of its poorer neighbours, such as India (6500) and Vietnam (2250). An important reason is the unavailability of trained surgeons. Although China has over 36,000 ophthalmologists, only a third are capable of performing independent cataract surgery. This shortfall is due in large part to a lack of hands-on training opportunities. For instance, a recent survey of residents at China's top-ranked resident training programs found that the median number of independent cataract surgeries performed was actually zero. The problem persists after formal training is completed and looks set to worsen as experienced surgeons retire: in recent years, <5% of cataract surgeries were performed by doctors aged 24-43 years. The problem is particularly acute in rural areas, where hands-on training opportunities for young ophthalmic surgeons are even rarer. One reason is safety concerns on the part of patients and senior doctors in entrusting operations to young surgeons.

New training models for cataract surgery are needed which can safely and efficiently support trainees during the transition from novice to competent surgeon. Simulation-based surgical training, using high-fidelity, inexpensive, re-usable model eyes have been successfully piloted. We now propose to study these in a randomized trial comparing a programme that combines training using these model eyes and training using traditional techniques versus traditional training alone, to assess the impact on quality of surgery (assessed by masked grading of videos using the ICO OSCAR system), visual acuity and cost-utility outcomes. We hypothesize that the hands-on training with the model eyes will be a valuable addition to the more didactic standard training.

The costs of our research will be minimised by piggybacking on an on-going collaborative program between Orbis International, the Chinese Ministry of Health (MOH), Chinese National Blindness Prevention Committee and Tongren Hospital (one of China's largest and best-respected eye hospitals), which will train 120 rural cataract surgeons at 60 county hospitals in 6 provinces. Our collaboration involves internationally-respected vision research teams at ICEH, Queen's University Belfast and Tongren; while offering opportunities for scale-up and engagement with Chinese policy makers at the highest level. This collaboration provides an excellent setting to assess whether model eye training can contribute to standard surgical training.

A successful trial proving the training benefits of inexpensive model eyes will make a unique contribution to building the capacity to manage China's leading cause of blindness, thus furthering the aims of SightFirst and the Chinese MOH, while improving the lives of Chinese people dwelling in low-resource areas.

# **Background Literature Review**

Some 90% of preventable blindness occurs in the developing world, and with the aging of populations globally, there is a rapidly increasing demand for well-trained ophthalmic personnel. Data from the International Council of Ophthalmology (ICO) reveal a shortage of ophthalmologists, with a shortfall predicted in both low income and developed areas.

China accounts for 18% of the world's blind, with an estimated 5 million people who have lost the ability to self-care, half of them due to un-operated cataract. The Chinese Ministry of Health has made it a priority to tackle preventable blindness nationally, but the estimated number of cataract operations performed annually (360,000) falls short of the number of people becoming blind each year from cataract (400,000). The cataract surgical rate (CSR) is the number of cataract operations per million population per year. China's cataract surgical rate of 1400 is far lower than that of India (6500) and Vietnam (2250), both of whom have lower per capita incomes.

In addition to the lack of access to affordable rural eye care and the aging Chinese population, an important cause of China's cataract problem is the lack of qualified ophthalmologists. Fewer than one third of the estimated 36,000 ophthalmologists in China perform cataract surgery, most concentrated in urban settings. Surgical quality among those who do operate is not always optimal, especially in rural areas.

The lack of hands-on training opportunities is an important barrier to achieving the Chinese government's goal of increasing cataract surgical capacity. A recent survey of residents at top-ranked training programs in China and Hong Kong found that the median number of cataract procedures performed during residency by Chinese trainees was 0 (compared to 100 for Hong Kong); falling well below mandated training minimums for other countries, such as 80-90 for Singapore and the United States and 350 for the United Kingdom. This problem of inadequate training opportunities persists after formal residency training is completed: in recent years, doctors aged 24-43 years performed <5% of operations across several specialities including ophthalmology, with two-thirds to three-quarters done by doctors over 50 years of age. The need to train a new cadre of young eye surgeons is particularly compelling in view of the fact that doctors at most of China's largest hospitals are civil servants, with a mandatory retirement age of 60. The problem has been ascribed in part to the unwillingness of senior physicians to accept responsibility for complications caused by junior surgeons.

Alternative training models that can safely build capacity among younger cataract surgeons are sorely needed. The problem is particularly profound in underserved rural areas. The Chinese Ministry of Health and Chinese Ophthalmic Society (COS) recently invited Orbis International to collaborate with Tongren Hospital, one of China's leading training centres, to carry out a project establishing a training curriculum for rural surgeons, which will include cataract surgical training for 120 rural doctors at 60 county hospitals in 6 provinces. Because of the opportunities it offers for scale-up and engagement with policy makers at the highest level, this Orbis-COS project has been chosen as the platform for the proposed research.

### Cataract Surgery

The procedure of sutureless scleral-tunnel small-incision cataract surgery (SICS) is one of the most commonly performed cataract surgery procedure in China, and is a main standard of care. The technique uses a smaller wound compared to the older technique of sutured extracapsular cataract extraction. There is less post-operative astigmatism, and fewer suturerelated problems for SICS. The clinical outcomes of phacoemulsification cataract surgery and sutureless extra-capsular manual SICS are comparable. SICS is an appropriate, safe, and affordable technique.

The primary outcome of cataract surgery is an improvement in visual acuity (VA). This can be measured without refractive correction (unaided), or with spectacle correction (best-corrected). It can be measured for distance (usually 6 metres) or near (usually 30cm). It is often very difficult, unrealistic, and expensive to measure post-operative visual acuity a few weeks after cataract surgery in rural LMIC settings due to the logistics of bringing the patient back to the hospital. Furthermore, there is evidence that day-one post-operative VA is a very good predictor of final VA. It is critical for surgeons to collect and analyse their own cataract surgical outcomes, as there is clear evidence that such monitoring and personal reflection improves surgical quality and outcomes. Tools for monitoring the outcomes and quality of cataract surgery have been developed, including post-operative VA, surgical complications,  and the ICO OSCAR (Ophthalmology Surgical Competency Assessment Rubric).

Complication rates vary for cataract surgery, depending on co-morbidity, the experience of the surgeon, the maturity of the cataract, and the technique used. Rates of complications (posterior capsule rupture (PCR) or vitreous loss (VL)) vary from 1.92% to 6%. The WHO recommends aiming for a complication rate (PCR rate) of <5%.

# Surgical Education and Simulation

It is of course of benefit to patients, trainees and trainers if simulation in surgical training offers and enables an accessible, safe, and reproducible method of learning surgical skills and procedures outside of the stress of the operating theatre. However, despite these explicit and implicit benefits, and the great enthusiasm surrounding simulation in surgical and certainly ophthalmic surgical training, a question remains: are the skills obtained transferable to theatre? Simply put, does practicing eye surgery on a simulator only make a trainee better at operating on a simulator, or does it make him/her better in the live-surgical setting too? This 'predictive validity', being the transfer of skills learnt in a simulation environment to live surgery, is challenging to measure.

Intensive simulation-based surgical education has been shown to rapidly increase surgical skills, decrease complication rates, provide a safe and relaxed environment to learn in, and enable sustained deliberate practice. However, this has not yet been demonstrated for ophthalmic surgical training in the context of a randomised trial.

Artificial eyes made from plastic and other synthetic materials have been used and developed over the past decade for ophthalmic simulated training. In the UK, Phillips Studio in Bristol have developed artificial eyes for use in training in a number of ophthalmic surgical procedures, including SICS and trabeculectomy. 'Kitaro DryLab' is a tool to teach and learn some steps of cataract surgery, including the capsulorrhexis. It is portable, and can be used

on a desktop, and without the need for an operating microscope (Frontier Vision Co. Ltd., Hyogo, Japan).

In a major systematic review, a team from Denmark screened over a thousand papers, and studied 118 trials involving simulation-based training or assessment of ophthalmic surgical skills among health professionals. They concluded that "using simulation models without knowledge of reliability, validity and efficacy may compromise patient safety, especially if the trained skills do not correlate with the skills needed for real-life performance". Through the use of state-of-the art frameworks for assessing the quality of trials, including a modern unified framework consisting of five sources of validity and a four-level assessment of the efficacy of simulation training programmes, they found the overall evidence for the use of simulation-based training or assessment in ophthalmology to be poor. Only two of the trials investigated transfer of skills into the operating theatre, and only four evaluated the effect of simulation-based training on clinically-relevant outcomes. More rigorous educational research investigating the validity, reliability and efficacy of simulation-based ophthalmic surgical training is needed.

# Rationale

The leading cause of blindness in China and the world generally is un-operated cataract. Despite notable efforts on the part of the Chinese government, China's cataract surgical rate (1400/million/year in 2015) remains behind that of many of its poorer neighbours. An important reason is the unavailability of a large enough number of trained surgeons. A recent survey of residents at China's top-ranked resident training programs found that the median number of independent cataract surgeries performed was zero.

Therefore, the huge need for eye surgery requires effective and efficient methods to meet the need to train eye surgeons. One way to achieve this might be through simulation-based surgical education, which has been shown to rapidly increase the rate of learning of surgical skills, decrease complication rates, and provide a safe and calm environment to learn in. However, this has not yet been robustly tested or proven for ophthalmology surgical training.

# **Project aims**

The aim of the proposed project is to provide an evidence base for a novel approach to cataract surgical training at the county-hospital level in China: the use of low-cost, high-fidelity model eyes. Thus, project aims are very tightly aligned with key SightFirst priorities in China: improving cataract surgical capacity, developing new training models and strengthening county-level facilities.

# **Objectives**

This study will assess whether the addition of simulation-based ophthalmic surgical education using bespoke artificial eyes is superior to standard conventional training alone; with regard to the initial acquisition of surgical competence, and surgery-specific outcomes (post-operative visual acuity). The outcomes will include measures of both surgical competence and surgical quality.

The overall purpose of this research is to develop the evidence base to guide efficient, highquality skills development in ophthalmic surgical training in China, which can then be scaledup to include other regions. The evidence base to be developed could inform the planning and implementation of ophthalmology surgical training programmes globally.

# Methodology

Study Design: Randomized controlled trial of an educational intervention.

Study Population: Cataract surgical trainees learning to perform small-incision cataract surgery (SICS) in the Orbis/Chinese Ophthalmic Society Rural Training Program (STEER). (This is a currently funded Orbis project, thus reducing the costs for this randomised trial.)

Partners: Orbis International and Queen's University Belfast ([name] is affiliated with both); Tongren Hospital and the Chinese National Committee for the Prevention of Blindness ([name] heads both); and International Centre for Eye Health at the London School of Hygiene & Tropical Medicine ([name], [name])

Sample Size Calculations: Based on OSCAR (ophthalmology surgical competency assessment rubric) scores for different surgical steps among SICS trainees at Aravind, India: 14 doctors in each of two groups operating on 10 patients each (total 280 surgeries) would allow for detection of a difference in mean OSCAR scores (across all steps) of 1.0 (point per set) between groups with a power of 0.9, alpha-error of 0.05, a standard deviation of 1.0 for scores, and an ICC of 0.57 for scores across cases within surgeon. The ICC value comes from our review of SICS cataract surgical training assessed using OSCAR in other Orbis training programs. (As this main outcome will be captured during surgery, there is no need to inflate our required sample size estimate to allow for loss to follow-up).

A total of 34 participants has been selected, to allow for a 15% attrition rate.

ICO-OSCAR scores cover 19 categories, with each category score ranging 0 to 5, and therefore with an overall 0 to 95. An example of a 1.0 point difference within the category, "Conjunctival and Corneal Tissue Handling" is for a Competent score (score = 5) the "tissue is not damaged nor at risk by handling," while for an Advanced Beginner score (score = 4), "tissue handling decent but potential for damage exists."

### Surgeon Inclusion Criteria:

- <20 complete SICS cases performed lifetime
- 25-50 years of age
- Completed ophthalmic training
- Will have opportunity to carry out independent SICS surgery after training

### Surgeon Exclusion Criteria:

- Already capable of performing independent intra-ocular surgery of any kind
- No opportunity to perform cataract surgery after training
- Unwillingness to discuss surgical training with colleague from other randomised group

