### Randomisation

#### Pre-randomisation baseline assessment

Following consent, participant surgeons will be evaluated. This will include evaluation of previous surgical experience, and introduction to the ICO OSCAR. They will then be assessed

using the baseline Simulation-OSSCAR (see Appendices 3a and 3b). This will involve three simulation procedures (these will be recorded, anonymised, and remotely assessed using the Simulation-OSSCAR). This provides the baseline score for all participants: intervention and control.

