#### Randomisation (stratified blocked randomization):

Participants who have reached the appropriate inclusion and exclusion criteria for the trial will be eligible for randomisation to 'intervention' or 'control'.

Eligible trainees completing baseline data collection will be enrolled into the study and stratified into 10 groups\* according to their training center and hospitals (home facilities). The hospitals with only one participant are combined to form a mixed group. Participants in each of the 10 stratified groups will be assigned at random to one of the study arms as shown in the following figure.

An independent statistician having no contact with participants will generate the randomization sequences (lists) using a computer system that is inaccessible until after recruitment. The random sequence includes three types: (1) A list of the mixed hospitals with only one participant; (2) A number of lists of the hospital with paired participants (3) Individual list(s) of the hospitals with more than two participants. Each random sequence comprises of sequence numbers and their corresponding codes (e.g. two letters plus a 4-digit number). Codes are used to represent the Intervention or Control group; a codebook is created for decoding the group allocations.

To preserve allocation concealment, a two-step procedure will be used for random allocation in each training center.

**Step 1**: Project manager (PM) sends randomization sequences to the Quality Control officer (QCO). QCO assigns a code to each participant from the randomization sequences. QCO update the random lists with participant's names and send it to PM. At the end of this step, neither the QCO or participants know what group the codes refer to.

**Step 2:** As soon as receiving result file from QCO, PM checks the codebook, update the file with participant's names and send it back to QCO. QCO allocates the participants into control and intervention groups and completes the random allocation.

The participants will know their group assignment. However, the staff(s) grading video recordings of assessments will be masked by having a randomized number assigned to each video.

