### **Prevention of Bias**

It is accepted that there will be variability in individual participants' inherent or natural surgical aptitude. In order to attempt to reduce the effects of this, the two groups will be balanced with regard to the baseline OSCAR scores of participants, and their total number of previous surgical cases. This however will only occur in final analysis, and not before randomisation or training.

All efforts will be made to standardise the training offered to the 'Intervention' participants. The intense simulation course will be held in the same Training Centres. The training will be conducted by experienced trainers who have undertaken a specifically designed 'Training the Trainers' course. All recordings of surgical procedures will be performed using the same recording system.

Video recordings of procedures will be allocated a random 7-digit number, and subsequently stored onto an encrypted computer, and a separate encrypted hard drive. This random number will be the only identifiable information available when the simulation/surgical procedure is assessed, thus masking the assessor to the participant's randomised group.

It is recognised that surgical education is complex and multi-faceted. However, every effort will be made to reduce 'contamination' bias. Participants will sign an informed consent form detailing that they will in no way share any of the details of the course or educational intervention with any surgeon who is not known to be in the same randomised group as themselves; for a minimum of six months following the end of the training programme in Tongren.

The PIs and co-investigators declare that they have no financial or other conflicts of interest that are relevant to this randomised trial.

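### The third surgeon exclusion criterion points the opposite way from the signed non-sharing undertaking and should be deleted or reversed

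*Combined protocol and SAP*

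**What the plan says.** The third item under Surgeon Exclusion Criteria removes a surgeon for "Unwillingness to discuss surgical training with colleague from other randomised group".

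Prevention of Bias, in its paragraph on contamination, states: "Participants will sign an informed consent form detailing that they will in no way share any of the details of the course or educational intervention". The people they may not share with are any surgeon "who is not known to be in the same randomised group as themselves", and the restriction runs "for a minimum of six months following the end of the training programme in Tongren".

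The criteria are a condition of entry. The section Randomisation (stratified blocked randomization) says: "Participants who have reached the appropriate inclusion and exclusion criteria for the trial will be eligible for randomisation". It adds: "Eligible trainees completing baseline data collection will be enrolled into the study and stratified into 10 groups". Consent comes before the baseline assessment: "Following consent, participant surgeons will be evaluated".

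The protocol uses the word course in two ways. The Intervention and Participant Information apply it to the training that both arms receive. Prevention of Bias also has: "The intense simulation course will be held in the same Training Centres".

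**The concern.** An exclusion for being unwilling to do something amounts to a requirement to be willing to do it. Read literally, the third item admits only surgeons prepared to talk about training with someone in the opposite arm. That is close to the conduct that the contamination paragraph sets out to prevent.

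The setting makes contamination a fair worry. Surgeons know their allocation, and colleagues from one hospital or training centre can be in opposite arms. If simulation content passed to controls, the comparison would be biased towards no difference. An eligibility rule that favours cross-arm discussion pulls against the plan's own safeguard, and whoever completes the screening form has no instruction on which text to follow.

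**Working it through.** No figure in the plan bears on this point, so the check is a reading of the two texts side by side.

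| | Surgeon Exclusion Criteria, third item | Prevention of Bias |
|---|---|---|
| Subject | Surgical training in general | Details of the course or the educational intervention |
| Conduct favoured | Talking across arms | Not sharing across arms |
| When it acts | Before randomisation, as an eligibility rule | From signature until at least six months after training ends |
| Stated purpose | None | To reduce contamination |

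1. **Direction.** The two favour opposite conduct. A trainee who says at screening that they would rather not discuss training with the other arm fails the third item, yet is behaving as the undertaking asks.

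2. **Force.** The randomisation section makes the criteria a condition of being randomised, so the item is an operative rule and not background text.

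3. **Is there a design reason for it?** The sections on outcomes, the intervention, follow-up and statistical analysis make no use of discussion between arms. The bullet is complete and grammatical, so lost text does not explain it. A reversed phrase is the likeliest cause, but that is an inference.

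4. **How far do the two conflict?** This turns on what the course means in the undertaking.
   - *If it includes the shared STEER training:* discussing training with the other arm is discussing the course. The conduct that one section requires surgeons to be willing to engage in is what the other forbids, and the conflict is full.
   - *If it means only the simulation training:* a trainee could discuss the shared training, withhold the simulation content and satisfy both sections. The criterion could still exclude someone who prefers not to discuss training at all.

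   The undertaking binds participants in both arms, and controls have no simulation training of their own to withhold. That leans towards the first reading, but the documents do not settle it.

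5. **What still restrains sharing?** Prevention of Bias places the undertaking in the signed consent form. Consent precedes the baseline assessment, and randomisation follows it. If that is the form signed at this stage, every randomised surgeon has given the undertaking. The third item tests willingness at entry and imposes no duty to talk afterwards.

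**The case against.** The strongest reply is that this is a slip of wording whose intent is plain from Prevention of Bias. The two sections do not cover the same subject, since surgical training is wider than the details of the course or intervention, and both arms share content that could be discussed without harm. The signed undertaking remains in force. The intervention is also about 16 hours that include supervised and repeated practice with feedback, most of which conversation cannot pass on, although simple exercises on apples or tomatoes could be copied.

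Most of this stands, and it limits the size of the point. It does not rescue the line, which is an eligibility rule pointing the wrong way with no stated purpose.

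Three stronger readings are tempting and are not supported:

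- *A reader might infer that the two sections cannot both be met.* That holds on only one of the two readings of the course.
- *A reader might infer that contamination control is missing, or that the trial loses power.* The undertaking is in the plan, the documents give no contamination rate, and nothing links this line to any change in the treatment difference.
- *A reader might size the problem by counting surgeons who have a fellow participant at their own hospital.* That count is the same whether the line is kept or removed. It also depends on how the 10 strata are made up. Assuming m mixed groups, and one hospital with at least two participants in each remaining stratum, the minimum is 2 × (10 − m). That is 18 of the 34 surgeons if m = 1, but 8 of 34 if m were 6. It does not measure the effect of this line.

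**Conclusion.** The third surgeon exclusion criterion is wrong as written; severity is low. It runs against the contamination safeguard, has no stated rationale, and could exclude the trainees most inclined to comply with that safeguard. That possible mis-screening is the direct harm, and nothing in the documents shows that it happened. No effect on power, sample size or the treatment estimate is claimed.

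The limited severity rests on the consent form carrying the undertaking, as Prevention of Bias says it does. The forms are not in the text available for review, so their wording could not be checked; that is not a gap in the plan. The opposite direction is clear from the text. The extent of the conflict, and the explanation that the phrase was reversed, are less certain and are for the sponsor to settle.

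**What to change.** 1. The sponsor confirms what the third item was meant to say.
2. Preferably, delete the line and refer to the undertaking in Prevention of Bias. Consent is already needed to take part, so if the form carries the undertaking, nothing is lost. If a criterion is wanted, reverse it, for example: *Unwillingness to agree not to share details of the training intervention with surgeons in the other randomised group.* This asks only for agreement, which can be established at screening.
3. State in Prevention of Bias whether the undertaking covers the shared STEER training, the simulation training or both.
4. Align the screening form, confirm that the consent form carries the undertaking, and check how surgeons already screened were assessed on this item.

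The cost is a one-line amendment, a clarifying sentence, and a check of the forms and of the screening records, for a trial with 34 selected participants. The sample size and the analysis do not change.
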